## 4. STUDY DESIGN

### 4.1. Overall Design

This is a Phase 2, multicenter, single arm, 12-week open-label proof-of-concept study of HTD1801 in adult subjects with PBC with an inadequate response to standard therapy. Inadequate response is defined as  $ALP \geq 1.5 \times ULN$  despite having been on adequate doses of UDCA for at least 6 months. Up to 30 subjects may be enrolled at up to 20 participating clinical sites.

Subjects may be pre-screened 28 to 56 days prior to the screening day visit using the central laboratory to confirm that their alkaline phosphatase is  $\geq 1.5 \times ULN$  and then will enter a screening period of up to 28 days prior to initiating therapy. Upon confirmation of eligibility, subjects will be enrolled and will receive HTD1801 1000 mg BID for 12 weeks. Study visits will occur at Day 0, Weeks 2, 4, 6, 8, and 12. A final follow-up visit will occur at Week 16, 4 weeks after the last dose of study drug. The Week 2, 4, and 8 visits may be performed remotely (home visits).

### 4.2. Scientific Rationale for Study Design

This is a single arm, open-label proof-of-concept study. All subjects will receive active study drug treatment. This study design is appropriate for a proof-of-concept study for an intervention in a new indication for PBC patients where the laboratory markers do not improve spontaneously and over time, are expected to get worse. Hence, seeing improvements, even without a control arm, is sufficient to meet the scientific goal of providing an indication of efficacy while also providing safety data.

### 4.3. Justification for Dose

The justification for the dose of HTD1801 selected for this study is based on HighTide's experience with this agent in previous clinical trials in other diseases. A Phase 1b/2a study was conducted in subjects with hyperlipidemia and a Phase 2 study was conducted in subjects with NASH. Even though these are different patient populations from the population to be evaluated in study HTD1801.PCT013, the observations from these studies help inform dose selection in PBC.

In the Phase 1b/2a study (study HTD1801.PCT004), in patients with hyperlipidemia, multiple ascending doses of HTD1801 500 mg, 1000 mg and 2000 mg per day were evaluated for up to 28 days. In this study HTD1801 2000 mg per day was effective in lowering serum cholesterol levels by approximately 11% ([name] 2020).

In the Phase 2 study in NASH (Study HTD1801.PCT012), two doses of HTD1801 were evaluated – 1000 mg per day and 2000 mg per day both given for 18 weeks. The dose of 2000 mg per day was effective in decreasing liver fat content and improving glycemic control, more so than the 1000 mg per day dose (Harrison et al. 2020).

In this same study, it was found that the relationship between decrease in liver fat content and body weight at baseline revealed no meaningful trends, implying that the pharmacodynamic changes associated with HTD1801 are relatively unaffected by body weight (see Figure 1; Study # HTD1801.PCT012) (Harrison et al. 2020).

The dose of HTD1801 to be used in this study, 1000 mg BID, is therefore expected be sufficient to show a preliminary treatment response in this 12-week study and also be generally well tolerated. HTD1801 has been shown in previous clinical studies, including in subjects with NASH and PSC, to have a favorable safety profile; gastrointestinal (GI) events were the most common adverse event in these studies; in the study in NASH 12% of subjects who received 1000 mg BID administration discontinued study drug due to GI events whereas there were no discontinuations due to these events in the study in PSC.

For the reasons cited above, the dosage of HTD1801 selected for this study (1000mg BID) is considered appropriate for use in the study population.

#### **4.4. End of Study Definition**

A participant is considered to have completed the study if he or she has completed all phases of the study including the last visit or the last scheduled procedure shown in the Schedule of Activities, Section 1.3.

The end of the study is defined as the date of completion of the last visit or procedure shown in the Schedule of Activities in the trial globally for the last subject in the study.

The end of enrollment if less than 30 subjects will be a collaborative decision between regulatory and Sponsor entities.

## 5. STUDY POPULATION

### 5.1. Inclusion Criteria

In order to be eligible to participate in this study, an individual must meet all of the following criteria:

1. Male or female between 18 and 75 years of age
2. Has a clinical diagnosis of PBC as confirmed by patient history consistent with the American Association for the Study of Liver Diseases (AASLD) Practice Guideline ([Lindor 2019](#)) confirmed by two of the following three criteria:
  - a. Biochemical evidence of cholestasis with elevation of ALP activity
  - b. Presence of antimitochondrial antibody (AMA)
  - c. Histopathologic evidence of nonsuppurative cholangitis and destruction of small or medium-sized bile ducts if biopsy performed

Note: historical AMA and liver biopsy data may be used, but must be recorded in source documentation.

3. Has been taking a stable, adequate dose (at minimum 13 mg/kg/day) of UDCA for at least 6 months with a serum ALP of  $\geq 1.5 \times$  ULN.
4. Has two consecutive values of ALP  $\geq 1.5 \times$  ULN (historical and screening values) of which the second ALP value must not be down trending relative to the first ALP value
  - a. If the historical ALP value was obtained more than 6 months prior to study start as part of standard of care, a more recent historical value should be obtained either using the local laboratory or alternatively, a chemistry sample can be submitted to the central laboratory as a part of an optional pre-screening visit. If this more recent value is  $\geq 1.5 \times$  ULN, the subject may be scheduled for a full screening visit as soon as 4 weeks later and a second ALP value should be obtained as part of full screening. Both values must be  $\geq 1.5 \times$  ULN.
  - b. If the historical ALP value was obtained less than 6 months prior to study start as part of standard of care, the subject may be screened and a second ALP value should be obtained as part of screening. There must be at least a 4-week interval between ALP values. Both values must be  $\geq 1.5 \times$  ULN.
  - c. If the screening ALP value is more than  $\geq 30\%$  lower than the historical value obtained as part of standard of care, the subject will not qualify for enrollment but may be re-screened as soon as 4 weeks later. If on re-screening the ALP value continues to be  $>30\%$  lower, the subject will not be included in the study. Because there may be considerable variability in the reference range for ALP obtained for the historical value, the estimation of downward trends of more than 30% should take this into account.
5. Be willing to discontinue UDCA the day prior to the start of IP dosing.
6. Be willing to discontinue the use of berberine supplements or berberine herbal products the day prior to the start of IP dosing

7. If the subject is taking cholestyramine or other bile acid sequestrant for pruritus, the subject must be on a stable dose and taking it no more than once a day for at least 8 weeks prior to Baseline visit. Must be willing and able to take cholestyramine at least 2 hours before or after study medication.
8. Females of child-bearing potential and males participating in the study must either agree to use at least two approved barrier methods of contraception or be completely abstinent from sexual intercourse, if this is their usual and preferred lifestyle, throughout the duration of the study and for three months after stopping study drug. Females who are postmenopausal must have appropriate documentation
9. Be able to understand and sign a written or electronic informed consent form (ICF)

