## **2.2. Study Rationale**

HTD1801 is a salt of ursodeoxycholic acid (UDCA) and berberine (BBR). UDCA has been the mainstay of primary biliary cholangitis (PBC) for many years and has dramatically improved the prognosis of the disease. UDCA is now registered around the world for the first-line treatment of the disease. Unfortunately, around 40 to 50% of PBC patients do not respond to UDCA or do not maintain an adequate response to UDCA. An inadequate response to UDCA is defined as a persistence of a biochemical cholestatic syndrome and is generally expressed as a persistent increase of serum alkaline phosphatase (ALP) above 1.67 times the upper limit of normal for the laboratory performing the analysis. Unfortunately, around 50% of PBC patients who are incomplete responders to UDCA do not respond to the addition of obeticholic acid. In addition, treatment with obeticholic acid may induce or exacerbate pruritus, a symptom frequently affecting PBC patients, and thus may lead to treatment discontinuation. Hence, there is still an unmet medical need in PBC patients.

The addition of BBR to UDCA, as a salt, in HTD1801 could deliver a benefit to PBC patients who are inadequate responders to UDCA alone. While BBR alone has not been studied in PBC, non-clinical data obtained with HTD1801 support studying the drug in PBC. In a rat model of cholestasis and liver inflammation, the bile duct ligation model, HTD1801 was effective in decreasing liver inflammation and necrosis, and improving bile duct health by reducing inflammation in the portal area and controlling bile duct proliferation. In addition, HTD1801 treatment was associated with an improvement in serum markers of cholestasis (ALP and GGT). In this model, UDCA generally gives mixed results and thus the improvement could be rationalized to come from the association of BBR and UDCA in HTD1801.

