17. Current or anticipated treatment with radiation therapy, cytotoxic chemotherapeutic agents, and immune-modulating agents (such as interleukins, interferons). Chronic, stable use of immunosuppressive medications may be allowed with medical monitor approval
18. Allergy to the clinical trial material or its components
19. Having received any experimental medications within 28 days prior to Screening
20. Use of bezafibrate or fenofibrate within 28 days prior to first day of IP dosing
21. Use of obeticholic acid (OCA) within 28 days prior to first day of IP dosing
22. Any other clinically significant disorders or prior therapy that, in the opinion of the investigator, would make the subject unsuitable for the study or unable to comply with the dosing and protocol requirements

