### **6.4.2. Prohibited Concomitant Medications**

#### **6.4.2.1. Prohibited medications that are active against PBC**

Use of the following medications, active against PBC, will be prohibited during the study from Baseline through 28 days after completion:

UDCA

Obeticholic acid

Bezafibrate

Fenofibrate

It is important to emphasize that subjects will be counseled before starting investigational drug and at each visit not to take both UDCA and/or berberine together with HTD1801, as HTD1801 contains both UDCA and berberine.

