### 12.2. Sample Size Determination

A sample size of 30 subjects provides  $\geq 90\%$  power for the primary endpoint assuming a mean percent reduction in ALP of 15% and a SD of 25%. Power calculations use a 5% one sided alpha and a t-test. Sample size calculation were performed in PASS ([PASS 2014](#)).

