2.3.1 Alkaline Phosphatase

ALP results are provided by the central and local laboratory with units of Units per Liter (U/L). Baseline is defined as the last available ALP result prior to treatment with change from baseline and percent change from baseline based upon this baseline value as the respective timepoint. Normalized ALP is defined as having ALP within the normal range (37 U/L to 116 U/L). Historical ALP will be summarized in the baseline characteristics table but not used otherwise.

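### Berberine use is allowed until the day before first dose, so any user's baseline can already contain both HTD1801 components, and no planned analysis would show it

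*Protocol*

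**What the plan says.** Inclusion 6 (Protocol 5.1, repeated in the synopsis) requires a subject to "Be willing to discontinue the use of berberine supplements or berberine herbal products the day prior to the start of IP dosing". Inclusion 5 words the UDCA rule the same way: "Be willing to discontinue UDCA the day prior to the start of IP dosing". UDCA, however, must also have been taken at a stable, adequate dose for at least 6 months (inclusion 3), whereas berberine has no minimum period of stable use and no dose limit. During treatment, Protocol 6.4.2.1 has subjects counselled "not to take both UDCA and/or berberine together with HTD1801, as HTD1801 contains both UDCA and berberine".

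Other agents get a longer interval. Exclusion 20 covers "Use of bezafibrate or fenofibrate within 28 days prior to first day of IP dosing" and exclusion 21 covers "Use of obeticholic acid (OCA) within 28 days prior to first day of IP dosing". Bile acid sequestrants need 8 weeks at a stable dose (inclusion 7).

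On the analysis side, SAP 2.3.1 states: "Baseline is defined as the last available ALP result prior to treatment". Protocol 9.1.2 applies the same rule to the secondary laboratory endpoints, which include lipids. SAP 2.5 makes every test and interval a one-sample comparison with baseline.

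Under SAP 3.2.3, a product stopped before the first dosing date counts as prior. Prior medications are listed; only concomitant ones are tabulated. The baseline characteristics (SAP 3.2.2) include the most recent UDCA dose, and SAP 3.3.3 plots ALP change by the ratio of current to prior UDCA dose. Nothing comparable exists for berberine.

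**The concern.** With no control arm, the pre-treatment value carries the whole inference. UDCA in that value is intended, because the population is defined by an inadequate response to it. Berberine is different. Protocol 2.2 explains that adding berberine to UDCA in the salt "could deliver a benefit to PBC patients who are inadequate responders to UDCA alone". A subject who took berberine up to the day before dosing has a Day 0 sample drawn on UDCA plus berberine. That subject's change to Week 12 measures a switch from two separate products to the salt, not the addition of berberine.

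If loose berberine lowers ALP or lipids, part of the effect is already in the baseline, and the subject pulls the mean percent change, the responder proportions and the lipid changes toward zero. In a proof-of-concept trial of up to 30 subjects, a few such subjects could blur the result that SAP 2.8 uses to judge whether a placebo-controlled study is warranted. The plan would give the reader no way to see that it had happened.

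**Working it through.** **Inputs from the documents.** Protocol 12.2: 30 subjects, power of at least 90%, "assuming a mean percent reduction in ALP of 15% and a SD of 25" per cent, one-sided 5% t-test.

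**Assumed inputs.** The documents give neither the number of berberine users, k, nor the share c of the HTD1801 effect already present in a user's baseline. Both are varied below.

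**The plan's own figure.** For a one-sample t-test with n = 30, df = 29, the critical value is 1.699 and the noncentrality is (15/25) × √30 = 3.286. Power from the noncentral t is 94.1%, so the stated figure reproduces.

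**With users in the sample.** Let p = k/30. Non-users have a mean reduction of 15% and users 15 × (1 − c)%. Then:

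- mean reduction = 15 × (1 − p·c)
- SD = √(25² + p(1 − p)(15c)²)

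Example with k = 3 and c = 0.5: p = 0.1; mean = 15 × 0.95 = 14.25; SD = √(625 + 0.09 × 7.5²) = 25.10; noncentrality = (14.25/25.10) × √30 = 3.11; power 91.8%.

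Power at n = 30:

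| Users (k) | c = 0.25 | c = 0.5 | c = 1 |
|---|---|---|---|
| 0 | 94.1% | 94.1% | 94.1% |
| 1 | 93.8% | 93.4% | 92.5% |
| 2 | 93.4% | 92.6% | 90.6% |
| 3 | 93.1% | 91.8% | 88.4% |
| 4 | 92.7% | 90.9% | 86.0% |
| 5 | 92.3% | 89.9% | 83.3% |

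With 3 users, the mean reduction falls from 15% to 14.6% (c = 0.25), 14.25% (c = 0.5) or 13.5% (c = 1).

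**Leaving flagged subjects out.** Removing 3 of 30 leaves n = 27, mean 15% and SD 25%. The noncentrality is 0.6 × √27 = 3.118 and power is 91.8%. Against the pooled analysis with 3 users, exclusion loses 1.3 points at c = 0.25 (93.1% to 91.8%), is level at c = 0.5 (91.8% both ways) and gains 3.4 points at c = 1 (88.4% to 91.8%).

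**Lipids.** The only figure available is the fall of about 11% in cholesterol in Protocol 4.3, which is for HTD1801 in hyperlipidemia. With 3 users of 30 and full carry-over it would become 11 × 0.9 = 9.9%. This is an illustration only.

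**The case against.** The strongest reply is that the effect may be nil. The number of users may be zero, and Protocol 2.2 says that berberine alone has not been studied in PBC. SAP 1.1 attributes a substantial part of the benefit to the interaction of the two moieties in the salt. Full carry-over from supplements of unspecified dose is therefore an extreme bound, and in the table every value below 90% except one (5 users at c = 0.5, 89.9%) depends on it. This stands.

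The primary objective concerns inadequate response to standard therapy, and the comparison with UDCA alone appears only in the rationale. A reader might infer that berberine users fall outside the target population. They do not: a user with ALP at or above 1.5 × ULN on adequate UDCA meets the population as written.

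A reader might also see a contradiction between one day for berberine and 28 days elsewhere. Exclusions 20 and 21 concern other drugs active in PBC, while inclusions 5 and 6 treat the two HTD1801 components alike. The contrast calls for an explanation but is not an error in itself. The 28 days in exclusion 19 run to Screening, so that item is no parallel.

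There are partial safeguards. Inclusion 4 requires a second ALP value that is not trending down, which limits recent starters. Protocol 6.4.2.3 sends supplements with interaction potential to the medical monitor, and exclusion 22 lets the investigator refuse a subject because of prior therapy. None of these removes a long-term, stable user. The prior-medication listing would let a reader trace users by hand, but no planned summary uses it.

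Finally, the expected bias runs toward no effect, and both documents call the p-values descriptive. That limits the harm to a weakened or misread signal.

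**Conclusion.** The point holds in a conditional form. If any berberine users enrol, their baseline can already contain both HTD1801 components, and the planned outputs would not show it. Dilution then depends on loose berberine being active, which the trial presumes and the documents do not demonstrate.

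For an assumed 3 users of 30, power is 93.1% to 91.8% if a quarter to half of the effect is already in baseline, and 88.4% at the extreme, against 94.1% with none. The stated 90% survives 2 users at full carry-over (90.6%) and 4 users at half (90.9%).

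A reader might infer that the ALP and lipid effects are diluted, or that the planned power is lost. The documents support neither statement, because they give no count of users and no ALP effect of berberine. This is an inexpensive improvement to interpretation, not a defect that undermines the primary analysis.

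**What to change.** In SAP 2.5.1.2 and 2.5.2, define a flag from the prior-medication records already collected: any berberine supplement or herbal product within 28 days before first dose, the look-back used in exclusions 20 and 21. Add the flag to the baseline characteristics in SAP 3.2.2.

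If any subject is flagged, report three results without flagged subjects as a sensitivity analysis: Week 12 percent change in ALP (mean, confidence interval, t-test), the ALP responder proportions and the lipid changes. Show them beside the all-subject primary result, which stays as planned.

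The cost is a paragraph of SAP text, one derived variable, one baseline row and one extra set of columns. The sensitivity analysis is slightly less precise (91.8% power if 3 of 30 are removed) and is not needed if nobody is flagged. The benefit is an estimate free of this bias and easier to interpret; power improves only if more than about half of the effect is already in users' baselines.

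Separately, the sponsor should reconcile the berberine interval in inclusion 6 with the 28-day intervals in exclusions 20 and 21. Which interval is right is for the sponsor to decide; none is proposed here.

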## 5.2. Exclusion Criteria

An individual who meets any of the following criteria will be excluded from participation in the study.

1. Uncontrolled concomitant autoimmune hepatitis (AIH). Subject should be on no more than 5 mg per day of prednisone (or equivalent dose for other corticosteroids) or no more than 150 mg per day of azathioprine at stable doses and serum ALT should be  $\leq 5 \times$  ULN. Use of medications other than prednisone or azathioprine for the treatment of AIH is prohibited (e.g., Mycophenolate). Stable use of immunosuppressives for other indications may be permitted (see below). Enrollment of subjects with controlled AIH will be limited to a total of 5 subjects.
2. Other plausible reasons for elevations in serum alkaline phosphatase such as drug-induced liver injury, concomitant cholestatic liver disease or bone disease.
3. History of alcohol or substance abuse
4. Prior liver transplantation or currently listed for liver transplantation
5. Presence of chronic viral hepatitis, types B or C.
6. Platelet count  $< 150,000/\text{mm}^3$ , albumin  $< 3.0 \text{ g/dL}$ , International Normalized Ratio (INR)  $> 1.2$ , or a history of ascites, or encephalopathy, or history of esophageal variceal bleeding
7. Total bilirubin  $> 1.3 \text{ mg/dL}$  unless subject has Gilbert's Syndrome. If subject has increased total bilirubin due to Gilbert's Syndrome, then direct bilirubin should be  $< 0.3 \text{ mg/dL}$ .
8. Hemoglobin  $< 10 \text{ g/dL}$  for males or females
9. Serum TSH level  $< 0.1$  or  $> 10 \text{ u/mL}$  (subject may be re-screened if hyper- or hypothyroidism has been corrected)
10. Renal impairment with eGFR  $< 60 \text{ ml/min}/1.73 \text{ m}^2$  (CKD stages 3, 4 or 5)
11. Human immunodeficiency virus (HIV)-1 or HIV-2 infection by history
12. Glucose-6-phosphate dehydrogenase (G6PD) deficiency. A screening assay will be performed. If serum level is below normal, clinical evaluation and further testing may be needed to confirm a diagnosis of G6PD deficiency.

13. History of malignancy within the past 2 years or ongoing malignancy other than basal cell carcinoma, or resected noninvasive cutaneous squamous cell carcinoma
14. Active, serious infections that require parenteral antibiotic or antifungal therapy within 30 days prior to Screening
15. Major surgical procedure within 30 days of Screening or prior solid organ transplantation
16. Females who are pregnant or breastfeeding
17. Current or anticipated treatment with radiation therapy, cytotoxic chemotherapeutic agents, and immune-modulating agents (such as interleukins, interferons). Chronic, stable use of immunosuppressive medications may be allowed with medical monitor approval
18. Allergy to the clinical trial material or its components
19. Having received any experimental medications within 28 days prior to Screening
20. Use of bezafibrate or fenofibrate within 28 days prior to first day of IP dosing
21. Use of obeticholic acid (OCA) within 28 days prior to first day of IP dosing
22. Any other clinically significant disorders or prior therapy that, in the opinion of the investigator, would make the subject unsuitable for the study or unable to comply with the dosing and protocol requirements

### **5.3. Screen Failures**

Potential subjects who do not meet all eligibility criteria at Screening will be allowed to rescreen once if the Investigator believes that there has been a change in eligibility status. If a potential subject fails to meet eligibility criteria upon rescreen, he/she will remain ineligible for the study.

